The Effect of Theraworx/[pH]uel on night-time cramps and spasm symptoms including quality of life, depression and sleep quality

[figure not shown]
NCT03159260

Date of Document: 2/1/2018

Protocol

Potential subjects were recruited through various targeted methods including newspaper ads, fliers in pharmacies and physician offices, social media, sleep disorder support groups and word of mouth. Individuals were excluded from the study if they were pregnant, have been previously diagnosed with a Restless Leg Syndrome (RLS), previously diagnosed with schizophrenia or any other neurological disorder. Individuals were included in the study if they reported experiencing night-time leg cramps on average at least three times per week. Eligible individuals were scheduled to attend an initial assessment (Baseline) at a community-based physical therapy clinic. During this visit the study was described by a member of the research team and the individual was asked to provide written consent to participate in the protocol (RB#: SSR.2016.3). Following providing informed consent, the subjects were asked to complete a series of questionnaires about their demographic characteristics, symptoms associated with NLC including sleep quality, quality of life and depression. Once these questionnaires were completed all subjects engaged in a 14-day no treatment period in which they were told not to change their usual activities and treatments. Each morning during the 14 day no treatment period subjects were asked to complete a Symptom Log on which they documented the frequency and severity of night-time cramps they experienced the previous night.

Subjects returned to clinic following this 14-day no treatment period (Post Control) and completed the same questionnaires excluding the demographic questions, since these demographic characteristics were not expected to change during the trial. Variables that were collected at the Post Control data collection point included the same measures of sleep quality, quality of life and depression as were collected at Baseline. Subjects were asked to refer their responses on these instruments to the previous 2 weeks following completion of the Baseline assessment. Once the subjects completed these instruments they were randomly assigned to one of two study groups by selecting 1 of 50 shuffled envelopes. Within 25 of these envelopes a card indicated "Foam A" and the remaining 25 envelopes contained a card indicating "Foam B." Subjects received two 3 ounce foam dispensers corresponding to their group assignment (Foam A or Foam B) and a 2-week Compliance and Symptom Log. The contents of these two foams remained blind to the subjects and the data collectors throughout the duration of the study until analysis. One of the foams contained Theraworx Relief™ (treatment) and the other contained a physiologically inert substance (placebo). Subjects were instructed to apply the foam they had been assigned to their entire upper and lower legs and feet using 8 pumps from the product dispenser per leg (upper thigh to foot) before retiring each evening for the next 14 days. If a subject experienced leg cramps after applying their assigned foam, they were instructed to reapply 2 pumps of the foam to the affected area in response to each event. Each morning during the 14 days in which subjects applied the foam they were asked to complete the Compliance and Symptom Log that documented the frequency and severity of night-time cramps and their use of the assigned foam they used to treat their night-time cramps the previous evening. Following 14 consecutive evenings of applying their assigned foam, subjects returned to the community clinic (Post Treatment), and return their completed Compliance and Symptom Log to the research staff. During this final visit subjects again completed the same measures of sleep quality, quality of life and depression that they completed during their Baseline and Post Control visits, referring their responses to the previous 2 weeks when they were applying the assigned foam to their legs. Subjects were compensated for completing the Baseline and Post Control and Post Treatment data collection visits.

Analysis:

Once all of the data were collected the contents of the foams were disclosed as Foam A containing the Placebo and Foam B containing the Treatment. The analysis was conducted in two phases. During phase 1 descriptive statistics were calculated to describe the demographic characteristics of the sample in order to assess the external validity of the results and the application of the findings to the larger population of patients suffering with NLC. Further descriptive analysis determined if the outcome variables met the assumptions of parametric statistics. The second phase of the analysis involved addressing the study hypotheses. Repeated measures analysis of variance (R-ANOVA) were calculated to determine if any of the outcome variables significantly ($p < .05$) differed between or within the two study groups over the duration of the study. Main or interaction effects detected by the R-ANOVA were explored further through calculating Tukey's post hoc comparisons. Finally, univariate comparisons (e.g. t-tests) determined if compliance rates or reported benefits differed between the study groups.

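### Current users of the test product are not excluded, and other products are neither restricted nor recorded in the foam period, so use of the active product in the placebo arm could go undetected

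*Combined protocol and SAP*

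**What the plan says.** **Eligibility (Protocol section, first paragraph).** The exclusions begin "Individuals were excluded from the study if they were pregnant, have been previously diagnosed with a Restless Leg Syndrome (RLS), previously diagnosed with schizophrenia" and end with any other neurological disorder. The one inclusion criterion is: "Individuals were included in the study if they reported experiencing night-time leg cramps on average at least three times per week". Neither mentions past or current use of the product under test.

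**Run-in (same paragraph).** After Baseline, every subject entered a 14-day untreated period, for which "they were told not to change their usual activities and treatments". No washout is described.

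**Randomisation and foam period (Protocol section, second paragraph).** Allocation comes after the run-in, at the Post Control visit: "Once the subjects completed these instruments they were randomly assigned to one of two study groups by selecting 1 of 50 shuffled envelopes". The envelopes are split 25 and 25 between Foam A and Foam B. The paragraph says how to apply the assigned foam. It says nothing about other treatments, and the daily log is described as covering cramps and use of the assigned foam only.

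**Blinding (same paragraph).** "The contents of these two foams remained blind to the subjects and the data collectors throughout the duration of the study until analysis". The placebo is described as inert. The text does not say whether the two foams match in look, smell or feel.

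**Analysis section.** Repeated measures ANOVA tests each outcome for differences between and within the groups over time, at p < .05.

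**The concern.** The product has a brand name in the second paragraph of the Protocol section and a second name in the title. Recruitment includes pharmacy fliers, social media and sleep disorder support groups. A volunteer with frequent cramps who already uses the product is therefore conceivable, and nothing in the criteria turns that person away.

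Two things are then at stake.

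- **The reference period.** A current user's Post Control values describe a treated fortnight, although the design treats it as untreated.
- **The comparison between arms.** A placebo subject who goes on using the branded product receives the active treatment, which pulls the two arms together. The log as described would not show it.

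All the efficacy outcomes (cramp log, sleep quality, quality of life, depression) are self-reported. No objective measure is described that could reveal the problem later.

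**Working it through.** The plan gives no sample size calculation, effect size, standard deviation or share of users, so there is no figure to reproduce. The check has three parts.

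**1. What the text allows in each period**

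| Period | Other treatments | Recording of other products |
|---|---|---|
| Run-in, before randomisation | Told not to change them | None described |
| Foam period, after randomisation | Not mentioned | None described; log covers the assigned foam |

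The instruction on usual treatments belongs to the first row. In that period no one is yet a placebo subject. Contamination of the placebo arm can arise only in the second row, where the text is silent.

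**2. Effect on the comparison**

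Assume a share u of each arm are current users, the product effect is Δ, and a user on their own supply gets all of Δ. Take the untreated mean as 0.

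*Users continue their own supply in the foam period.*
- Post Treatment means: active Δ, placebo uΔ. The difference is Δ − uΔ = (1 − u)Δ.
- Mean change from Post Control: active (1 − u)Δ, because users were already treated; placebo 0, because users are treated at both times. The difference is again (1 − u)Δ.

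*Users stop their own supply when given the assigned foam.*
- Mean change: active (1 − u)Δ, placebo −uΔ. The difference is (1 − u)Δ + uΔ = Δ.
- The contrast between arms is then unbiased, but both within-arm changes are shifted by −uΔ. The plan tests changes within groups as well as between them.

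So (1 − u) is the worst case under this model. With all 50 envelopes drawn (25 per arm):

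- 1 user per 25: 1 − 1/25 = 0.96
- 3 users per 25: 1 − 3/25 = 0.88
- 5 users per 25: 1 − 5/25 = 0.80

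**3. What that could cost in power (illustration only)**

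Assume a true effect of 0.8 SD, a two-sided 0.05 level (the plan does not state sidedness), 25 per arm, and a simple two-group comparison of means by normal approximation. Power = Φ(d(1 − u)√(25/2) − 1.96).

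| u | Effect (SD) | Power |
|---|---|---|
| 0 | 0.800 | 80.7% |
| 1/25 | 0.768 | 77.5% |
| 3/25 | 0.704 | 70.2% |
| 5/25 | 0.640 | 61.9% |

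The two-sample t-test gives 79%, 76%, 68% and 60%. For an assumed effect of 0.5 SD, power by the normal approximation falls from 42.4% at u = 0 to 29.3% at u = 5/25. These figures are not predictions for this trial, because neither u nor the effect is known.

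**The case against.** **No user is documented.** A brand name does not show that these volunteers could buy the product or that any had used it. This stands: the gap in the text is certain, its effect on the data is not.

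**The dilution model is harsh.** Entry requires cramps at least three times a week on average. A current user who benefits well is less likely to qualify, and those who do qualify are more likely to be poor responders. The model also needs users to keep applying their own supply in addition to the assigned foam. This stands too, and is why (1 − u) is given as a bound and not an estimate.

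**Stronger readings.** A reader might infer three things that the documents do not support.

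- *That subjects were told to keep their usual treatments while on placebo.* The instruction is given for the run-in, which ends before randomisation.
- *That experienced users recognised their foam and were unblinded.* Blinding is stated and the foams were coded. Silence on matching makes recognition possible, but it is not evidence of a mismatch. For scale, if 12% recognised their foam and shifted their ratings by 0.5 SD, the bias would be 0.12 × 0.5 = 0.06 SD if one arm were affected, or 0.12 SD if both were, in opposite directions. The standard error at 25 per arm is √(2/25) = 0.28 SD. Both inputs are assumptions.
- *That people who liked the product were the most likely to volunteer.* Nothing says that the advertisements named the product.

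**Excluding every past user goes too far.** It would narrow the external validity that the Analysis section sets out to assess. This is a fair point; the case for exclusion is clear only for current users.

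**It may be too late.** The document is in the past tense and says that the foam contents were disclosed once data collection ended. A new exclusion could not then be applied, and asking about use after disclosure would invite recall bias. This limits the remedy for this trial but does not remove the gap.

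**Conclusion.** The point holds in limited form. The criteria do not exclude current users of the test product. The run-in instruction would leave such a user treated in the reference period. The silence on other products in the foam period means that use of the active product in the placebo arm would be neither prevented nor detected.

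The consequence for the comparison is dilution by at most (1 − u): 4%, 12% or 20% of the effect for 1, 3 or 5 continuing users per 25. This assumes equal shares in both arms and a full product effect in users. The actual share is unknown and could be zero. Foam recognition by past users would probably push self-reported outcomes the other way, in favour of the product, but it remains an inference.

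This is a cheap improvement. It is not a demonstrated flaw in the result.

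**What to change.** - Add current use of Theraworx/[pH]uel, in any form, to the exclusions in the first paragraph of the Protocol section.
- Ask about current and past use at Baseline, and again at Post Control before the envelope is drawn.
- Tell subjects not to use the test product other than as the assigned foam.
- Add one item to the Compliance and Symptom Log for any other cramp product used.
- State whether the two foams match in look, smell and feel.
- Keep past users in the main analysis, and repeat the Foam A versus Foam B comparison without them as a sensitivity analysis.

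The cost is a few volunteers lost, a short question at two visits that already take place, and one extra log item.

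If enrolment is complete and product use was recorded, report it by arm and run the sensitivity analysis. If it was not recorded, state this as a limitation: undetected use in the placebo arm would bias the comparison towards no difference, and its extent cannot be established.

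### At least five outcomes are tested at p < .05 with no leading outcome, fallback or fixed univariate test shown; disclosing the foams before analysis is a secondary issue

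*Combined protocol and SAP*

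**What the plan says.** The outcomes are described in the Protocol section. In the daily log, "they documented the frequency and severity of night-time cramps they experienced the previous night". At the last clinic attendance, "subjects again completed the same measures of sleep quality, quality of life and depression that they completed during their Baseline and Post Control visits". That makes at least five outcomes, and none is called primary.

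The Analysis section opens with disclosure: "Once all of the data were collected the contents of the foams were disclosed as Foam A containing the Placebo" (the treatment being in the other foam). The next sentence is "The analysis was conducted in two phases". In phase 1, "Further descriptive analysis determined if the outcome variables met the assumptions of parametric statistics"; no criterion is given, and no method if the check fails. In phase 2, "Repeated measures analysis of variance (R-ANOVA) were calculated to determine if any of the outcome variables significantly" differed, at p < .05, between or within the groups. Tukey comparisons follow any effect found. Last, "univariate comparisons (e.g. t-tests) determined if compliance rates or reported benefits differed between the study groups".

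On blinding, the Protocol section says only that the foam contents "remained blind to the subjects and the data collectors throughout the duration of the study until analysis". The analyst is not mentioned.

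**The concern.** Three choices are left open in the text: which outcome leads, what replaces the parametric analysis if its assumptions fail, and which test is used for compliance and reported benefits. The document is short and supplies these rules nowhere else.

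The first choice has the most room. When a significant difference on any of several outcomes can carry the conclusion, the chance that at least one arises with no true effect is well above 5%. A reader cannot tell whether an emphasised outcome was the intended one or the one that came out best.

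The order of disclosure adds a smaller doubt. As written, the identities are known before the assumption checks and before every test. Choices not yet fixed could then be settled by someone who knows which direction favours the product.

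**Working it through.** The plan states no error rate across outcomes, so there is no figure of its own to reproduce.

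**Inputs from the document.** Five outcomes as a minimum; threshold p < .05; 25 envelopes per foam.

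**Assumptions not in the document.** No true effect. Two-sided tests: sidedness is not stated, although the plan speaks of groups differing. One test per outcome, with a t-test on change (25 + 25 - 2 = 48 df) standing in for the R-ANOVA. Equal positive correlation between outcomes, from 0 to 0.8, with all outcomes scored in the same direction.

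**Step 1: is the code needed for the tests?** No. Every planned comparison is between or within two groups and runs equally well on the labels A and B. Swapping the labels leaves two-sided p-values unchanged. Identity is needed only to read the direction of a difference.

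**Step 2: leading outcome, independent outcomes.**
- One fixed outcome, false positive favouring the product: 0.05 / 2 = 2.5%, code open or closed.
- Any of five significant in either direction: 1 - 0.95^5 = 22.6%.
- Leading outcome open, code closed, smallest p-value leads: by symmetry half favour the product, 22.6% / 2 = 11.3%.
- Leading outcome open, code open, any product-favouring result leads: 1 - 0.975^5 = 11.9%.

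Of the rise of 11.9 - 2.5 = 9.4 points, 11.3 - 2.5 = 8.8 points are present with the code closed. Disclosure accounts for the remaining 0.6.

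**Step 3: correlated outcomes.** Simulation with 200,000 null trials per scenario, 25 per arm; false positives favouring the product:

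| Correlation | Code closed | Code open |
|---|---|---|
| 0 | 11.3% | 11.8% |
| 0.2 | 11.0% | 11.2% |
| 0.3 | 10.4% | 10.4% |
| 0.5 | 9.3% | 9.3% |
| 0.7 | 7.5% | 7.5% |
| 0.8 | 6.5% | 6.5% |

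One fixed outcome gave 2.4% to 2.5% throughout.

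**Step 4: what the closed-code column assumes.** It supposes that the leading outcome is picked by smallest p-value before the code is opened. If outputs are finalised as A versus B but the outcome to emphasise is chosen after opening, the open-code figures apply again.

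**Step 5: open fallback, one outcome.** Simulation with 20,000 null runs per distribution, 25 per arm, two-sided. Taking the smaller p-value of the t-test and the Mann-Whitney test gave 5.5% (normal), 6.5% (lognormal) and 6.8% (negative binomial). Adding a log-scale t-test gave up to 7.3%. That is at most about 7.3 - 5 = 2.3 points above nominal, against 22.6 - 5 = 17.6 points for any of five independent outcomes on the same two-sided scale.

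**The case against.** The strongest reply is that disclosure timing hardly matters. It adds at most 0.6 points, and nothing visible at correlations of 0.3 and above. The self-reported data were collected with subjects and data collectors blind, so later disclosure cannot alter them. R-ANOVA and Tukey are named without condition, so the main method is not open. The order is read from the sequence of sentences in a brief retrospective account, which does not say to whom the contents were disclosed. All of this stands, and it is why disclosure is secondary here.

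It does not answer the missing rules. Those gaps exist with the code open or closed, and naming R-ANOVA does not say which outcome's R-ANOVA decides.

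A reader might infer three stronger things:
- That outcomes or tests were in fact chosen with knowledge of the code. The document does not show this; it does not say whether the analyst knew the code or when choices were made.
- That early disclosure by itself raises the false-positive rate. Under fixed rules it changes nothing.
- That keeping the code closed would settle the matter. It would not, because a favourable outcome can still be emphasised once the code is opened.

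**Conclusion.** The concern holds for the missing rules, chiefly the missing leading outcome. Leaving it open raises the chance of a product-favouring false positive from 2.5% to somewhere between about 6.5% (correlation 0.8) and 11.9% (independent outcomes with the code open). Disclosure before analysis, with analyst blinding unstated, is a minor addition of at most 0.6 points.

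These are illustrations, not estimates for this trial. They rest on the assumed correlations, on simple two-group tests in place of the R-ANOVA, and on a pure selection rule. Five is a minimum count: separate group, time and interaction effects, any subscales, compliance and reported benefits would add tests.

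**What to change.** **If the analysis is done**, as the past tense suggests, leave the disclosure sentence where it is, since moving it could misstate what happened. Add a short statement of whether the analyst knew the code and when the analysis rules were fixed. Label as post hoc and unblinded any choice of leading outcome, fallback or univariate test not fixed before disclosure. The cost is a reporting statement.

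**If the analysis is not yet done**, fix the following before disclosure:
- one leading outcome, for example cramp frequency, on which entry to the study is based, with the others secondary;
- one test and one fallback per outcome, with the criterion that triggers the fallback;
- one named test each for compliance and for reported benefits.

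These rules are the effective remedy. As a supplement, have someone outside the analysis hold the key, run phases 1 and 2 as Foam A versus Foam B, and disclose only when those outputs are final.

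The cost is a key-holder, a short delay in disclosure and a weaker claim for the non-leading outcomes. No added subjects, visits or data are needed.

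### Cramp frequency is tested by an unadjusted R-ANOVA on raw values; for a 14-night total, a log-scale comparison adjusted for the control-period count would have clearly more power

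*Combined protocol and SAP*

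**What the plan says.** The Analysis section of the combined protocol and SAP names one method for all outcomes: "Repeated measures analysis of variance (R-ANOVA) were calculated to determine if any of the outcome variables significantly", continuing "significantly ($p < .05$) differed between or within the two study groups over the duration of the study". Follow-up is by pairwise tests: "Main or interaction effects detected by the R-ANOVA were explored further through calculating Tukey's post hoc comparisons". Before that, in phase 1, "Further descriptive analysis determined if the outcome variables met the assumptions of parametric statistics". No criterion is given for that check, and no alternative method if an outcome fails it.

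Cramp frequency comes from morning logs kept for the 14-day no-treatment period and for the 14 days on foam. The second log "documented the frequency and severity of night-time cramps and their use of the assigned foam". Entry requires "night-time leg cramps on average at least three times per week", a lower limit with no upper one. Subjects were "randomly assigned to one of two study groups by selecting 1 of 50 shuffled envelopes", 25 per foam. The text does not say whether the analysed variable is a total, a weekly rate, a nightly mean or a number of nights with cramps. It gives no cramp distribution and no sample-size calculation.

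**The concern.** Sleep quality, quality of life and depression are questionnaire outcomes. Cramp frequency, if it is a total, is a count with a floor at zero and no ceiling. It is also the outcome closest to the trial's question. Two features of the named test cost power for such a count:

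- It works on raw change. If the foam removes a percentage of cramps, the absolute change grows with the starting rate, and the test treats that growth as noise around one common shift.
- It subtracts the control-period count with a coefficient fixed at 1. When counts fall in both arms and each 14-night count is itself noisy, the best-fitting coefficient is below 1, so plain subtraction adds noise.

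With about 50 subjects there is little power to spare, and a null result on raw change would be hard to interpret.

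**Working it through.** **What the documents supply.** 25 per arm if all 50 envelopes are used; p < .05 (taken as two-sided); two 14-night logging periods; entry at 3 or more cramps per week, that is 6 per 14 nights. They state no power or effect size, so there is no figure to reproduce. For context, 25 per arm gives 80% power only for a standardised difference of 0.79, and 42% at 0.5.

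**Form of the test.** With one control-period and one treatment-period total per subject, the R-ANOVA group-by-time interaction is the two-sample t-test on change = treatment total - control total.

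**Why scale matters.** Take reductions of 50% (Foam B, treatment) and 20% (Foam A, placebo), and ignore the added constant.

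| Starting rate | 14-night total | Change, Foam A | Change, Foam B | Difference |
|---|---|---|---|---|
| 3 per week | 6 | -1.2 | -3 | -1.8 |
| 20 per week | 40 | -8 | -20 | -12 |

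On the log scale the difference is the same for both subjects: ln(0.5) - ln(0.8) = ln(0.625) = -0.47.

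**Simulation, main scenario.** All of these inputs are assumptions: weekly rates lognormal with median 5 and log SD 0.3-0.8, entry at 3 or more, period-to-period log SD 0.25-0.4, Poisson counts, reductions of 50% versus 20%, no dropout. Ranges cover all spread settings and repeated sets of runs.

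| Analysis of the 14-night total | Power |
|---|---|
| Raw change (interaction as planned) | 30-55% |
| Change in log(count + 0.5) | 50-78% |
| Raw count, control-period count as covariate | 58-88% |
| Log count, log control-period count as covariate | 66-82% |

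Log change gained 14-30 points over raw change. Under no effect, both rejected in 4-6% of trials. Once the covariate is in, raw and log differ by only about -3 to +7 points.

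**Second scenario, different noise model.** Median 10 per 14 days before truncation at 6, gamma period noise with variance 0.15, placebo factor 0.8, rate ratio 0.6, 6,000 trials per cell:

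| Log SD of rates | 0.2 | 0.5 | 0.8 | 1.1 |
|---|---|---|---|---|
| Raw change | 43% | 42% | 37% | 31% |
| Log change | 58% | 61% | 63% | 65% |
| Raw with covariate | 84% | 76% | 68% | 60% |
| Log with covariate | 78% | 74% | 71% | 72% |

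At log SD 0.5, moving to logs alone adds 61 - 42 = 19 points, while adding the covariate alone adds 76 - 42 = 34. At log SD 0.8 the figures are 26 and 31. Only at 1.1 does the scale give more (34 against 29). Over all 12 spread and noise settings at rate ratio 0.6, raw change trailed log change by 10-41 points, and its type I error over the null settings was 3.8-5.2%.

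**Share carried by the most extreme subjects.** In this second scenario with no foam effect, the 5 most extreme of 50 carry 46%, 52%, 61% and 72% of the residual sum of squares of raw change at log SD 0.2, 0.5, 0.8 and 1.1. For normal data the share is about 44%.

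**If the variable is cramp-nights out of 14.** Main-scenario rates and effects, at log SD 0.3, 0.5 and 0.8, each with period SD 0.25 then 0.4. Raw change: 59, 45, 60, 45, 66, 51%. Log change: 64, 50, 65, 49, 66, 50%. The gain is -1 to +5 points here, and -2 to +5 over repeated runs. With the covariate, raw beat log by 4-7 points.

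**The case against.** The strongest reply is that nothing here is invalid. The raw-change test holds its type I error, a mean difference in cramps is a legitimate and readable quantity, and phase 1 does look at assumptions. The first two statements stand: this is a matter of efficiency. The third does not help, because no action follows from the check.

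A second reply is that the size is wholly assumed. That also stands. The documents give no rate, spread, effect or placebo response, and the result depends on an endpoint definition they omit. For cramp-nights the scale argument nearly disappears.

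A third reply is that the scale is the lesser issue. Over the spreads in the main scenario this is largely right for a proportional effect: the covariate alone recovers most of the loss. A fix confined to the log transformation would leave the larger gain unused.

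A reader might infer from the open-ended entry criterion that a few heavy crampers dominate the raw changes. The documents do not support that as a statement of fact. It would need a wide spread of rates, and none is reported. With narrow spread the concentration is hardly above that of normal data, yet raw change still loses 58 - 43 = 15 points to log change.

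**Conclusion.** The point holds as a low-cost improvement. If cramp frequency is the 14-night total, the test as written has roughly 30-55% power under the stated assumptions, against 50-78% for log change and about 66-82% for the log count with the log control-period count as covariate. Raw change had less power than log change in every spread and noise setting tried for 14-night totals with a proportional reduction. Most of the loss comes from using unadjusted raw change.

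Two stronger readings should be resisted. The plan does not inflate false positives. Nor can the full gain from logs be claimed whatever the endpoint: it applies to totals analysed as unadjusted change, and it shrinks to a few points for cramp-nights or, with a proportional effect, once the covariate is in. All power figures assume 25 per arm with no dropout and rest on assumed rates.

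**What to change.** 1. Define the cramp endpoint: the total over the 14 nights, scaled to nights logged (total x 14 / nights logged).
2. Compare Foam B with Foam A by regressing log(treatment-period count + 0.5) on foam group and log(control-period count + 0.5).
3. Report exp(group coefficient) as a ratio with 95% CI, and give raw means by group and period for description.
4. Because the Analysis section describes the contents as disclosed and the analysis as conducted, label this a supplementary analysis and report it beside the planned R-ANOVA.

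If the variable used was cramp-nights out of 14, say so; the control-period covariate on the raw scale is then enough. A Wald test from a negative binomial model is not advised at this size without a small-sample correction: its type I error was 6-9% in one set of simulations and reached 8.4% in another.

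The cost is small, since the data already exist. The effect becomes a percentage reduction instead of cramps avoided, and a small constant is added to handle zero counts.

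### The planned R-ANOVA and a single Post Treatment visit tied to 14 evenings of foam can turn the randomised comparison into one of completers, with bias possible in either direction

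*Combined protocol and SAP*

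**What the plan says.** The Analysis section names one model for the outcomes: "Repeated measures analysis of variance (R-ANOVA) were calculated to determine if any of the outcome variables significantly" differed, at p < .05, between or within the two groups over the study. Tukey comparisons follow any effect found. A separate sentence says that "univariate comparisons (e.g. t-tests) determined if compliance rates or reported benefits differed between the study groups". There is no analysis set, missing-data method, dropout allowance or sample-size calculation.

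The Protocol section sets the order of events. Baseline and Post Control questionnaires come before allocation: "Once the subjects completed these instruments they were randomly assigned to one of two study groups by selecting 1 of 50 shuffled envelopes". The envelopes are split 25 and 25. The final visit is introduced with "Following 14 consecutive evenings of applying their assigned foam, subjects returned to the community clinic (Post Treatment". At that visit subjects "return their completed Compliance and Symptom Log to the research staff", and "During this final visit subjects again completed the same measures of sleep quality, quality of life and depression". The document describes no visit, and no other route for returning the log, for a subject who gives up the foam before day 14.

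**The concern.** Two features combine. A classical repeated measures ANOVA needs a full row for each subject. Every post-randomisation value, questionnaire or log, also reaches the trial through one visit, and that visit is described only for subjects who finished the course. A randomised subject who stops and does not come back therefore leaves the analysis without any rule having decided so.

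Giving up a foam that seems not to work is plausibly related to outcome. If this happens more in one arm, the subjects left are no longer the groups that randomisation formed. Poor responders lost from the active arm make the foam look better than it is. Poor responders lost from the placebo arm make placebo look better and hide a real effect. With 25 per arm, a 20% loss is five subjects.

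**Working it through.** **What can be missing.** Consent and the Baseline questionnaires come first, and the envelope is drawn only after the Post Control questionnaires. A randomised subject has therefore attended both earlier visits, and only Post Treatment can be missed. Loss before Post Control precedes randomisation and cannot bias the randomised contrast.

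**Figures to reproduce.** None. The plan states no power, effect size, SD or dropout rate. From the documents: 25 per arm and alpha 0.05 (two-sided assumed). Everything else below is an assumption.

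**Loss unrelated to outcome.** Power = Φ(d·√(n/2) − 1.96), with d = 0.8 SD:

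- n = 25: Φ(2.828 − 1.96) = 80.7%
- n = 23: Φ(2.713 − 1.96) = 77.4%
- n = 20: Φ(2.530 − 1.96) = 71.6%
- n = 18: Φ(2.400 − 1.96) = 67.0%

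This loses power but adds no bias.

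**Loss related to outcome, questionnaire-type score.** Simulation with 10,000 trials per scenario, SD 1, correlation 0.5 between visits, lower score better. Dropout is more likely with a worse change score, and completers only are analysed. The two-visit test is a t-test on change from Post Control to Post Treatment. The three-visit test is the classical group-by-time F test.

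| Scenario | Estimate (SD) | Rejection, two visits | Rejection, three visits |
|---|---|---|---|
| No effect, no loss | 0.00 | 5.3% | 5.1% |
| No effect, 10% of active lost | −0.13 | 8.5% | 7.9% |
| No effect, 20% of active lost | −0.23 | 13.5% | 10.8% |
| No effect, 30% of active lost | −0.34 | 20.0% | 15.3% |
| No effect, 20% lost in both arms by the same mechanism | 0.00 | 8.3% | 7.2% |
| Effect −0.80, no loss | −0.80 | 79% | 83% |
| Effect −0.80, 10% of placebo lost | −0.68 | 64% | 72% |
| Effect −0.80, 20% of placebo lost | −0.56 | 49% | 58% |
| Effect −0.80, 30% of placebo lost | −0.46 | 36% | 46% |

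**Loss related to outcome, cramp log.** Simulation with 4,000 trials, Poisson counts with gamma-distributed rates (mean 8 per 14 nights, shape 2), and dropout after week 1 ranked on lack of improvement.

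- No true effect, 5% of placebo and 15–20% of active lost: completers-only analysis is biased by 0.5–0.7 cramps per 14 nights towards the foam, with type I error of 11–13%. If the logged nights of those who left are in hand and used, bias is 0.2–0.3 against the foam and type I error is 4–5%.
- True 40% reduction, 20% of placebo and 5% of active lost: completers only gives −2.3 (power 73%) and logged nights −3.5 (power 91%), against −3.2 with everyone followed. Another build of this count model gave −1.7 with 40% power for completers and −3.0 with 66% for logged nights, against −2.8. The direction is stable, but the level depends on the model.

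Logged nights are not free of bias either. They overshoot a little because they keep the poor first week of those who left and never see their second week.

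**The case against.** Much of the case on the other side stands.

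- The 14-evening wording may simply describe the schedule. A reader might infer a rule that excludes anyone who missed an evening. The documents state no such rule, and the planned comparison of compliance rates implies that partly compliant subjects could attend and be analysed. The gap concerns subjects who stop and do not return.
- Listwise deletion is the default of classical R-ANOVA. The document does not say that it was applied.
- A reader might infer that a missed Baseline or Post Control visit also removes a randomised subject, and so compound losses over three visits. The visit order rules this out.
- Subjects were blinded to the foam. With no true effect, dropout for lack of benefit should be similar in both arms, so the false-benefit scenario needs some other difference between the foams. The hidden-benefit scenario needs only that an inert foam disappoints more often. Equal loss by the same mechanism gave no mean bias, although rejection still rose to 7–8%.
- A different model alone would not cure the problem. Each questionnaire has one post-randomisation value, so a mixed model recovers little when that value is missing. Partial logs help only if someone retrieves them, and the plan describes log return only at the final visit.

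None of this removes the core point. The plan does not say who is analysed, or whether a subject who stops is still assessed.

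**Conclusion.** The concern holds as a weakness of the plan. With R-ANOVA on complete rows and all post-randomisation data collected at one visit, a randomised subject who stops early and does not return drops out of the comparison. Bias in either direction is then possible, but only if loss is related to outcome and differs by arm.

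Its actual size is unknown. The document reports no dropout, treatment lasts 14 days, and bias from this source is nil if all 50 subjects returned. A reader might infer that the trial's result is biased; the documents do not support that. The simulated figures rest on assumed loss rates, effect sizes and dropout mechanisms, and show only that a few lost subjects matter at this sample size. The change should be made, with medium confidence in its practical importance.

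**What to change.** 1. State that all randomised subjects are analysed in the group they drew.
2. Hold the Post Treatment assessment at the end of the 14-day window for every randomised subject, whether or not foam use continued, and collect the log then, complete or partial. This is the main remedy; the modelling changes cannot replace it.
3. Analyse cramps per logged night, adjusted for the rate in the 14-day run-in. In the count simulation with a true effect and no dropout, run-in adjustment alone raised power from 79% to 91%.
4. Analyse each questionnaire at Post Treatment, adjusted for the Post Control score.
5. Report losses and reasons by arm, and add one sensitivity analysis that gives unfavourable values to subjects without Post Treatment data.

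The document is written in the past tense. If follow-up is already over, items 1, 3, 4 and 5 can still be applied to the data and logs that were retained.

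The cost is analysis wording and keeping a visit that is already planned, with no extra subjects or instruments. One small downside is that the estimate becomes a treatment-policy effect, which may be slightly smaller than the effect among those who complete the course.
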